5.0 ANALYSIS ENDPOINTS

The primary endpoints include:

Phase 1b

- Adverse events, SAEs, assessments of clinical laboratory values, vital sign measurements, physical examination findings, and electrocardiograms (ECGs).

Phase 2

- CBR-16.

5.1 Secondary Endpoints

The secondary endpoints include:

- Clinical benefit rate at 24 weeks (CBR-24 is defined as the proportion of patients who achieve CR or partial response of any duration or have SD at 24 weeks).
- Overall response rate (ORR; defined as best response of CR or partial response).
- Progression-free survival (PFS).
- Overall survival (OS).
- Change in tumor size from baseline.
- Steady-state PK parameters of MLN0128 and exemestane including, but not limited to, single-dose maximum (peak) concentration (C_{max}), T_{max} , area under the plasma concentration versus time curve from zero to 24 hours (AUC_{24h}), area under the plasma concentration versus time curve from zero to the last measurable concentration (AUC_t), and $t_{1/2}$.
- Adverse events, SAEs, assessments of clinical laboratory values, vital sign measurements, physical examination findings, and ECGs.

5.2 Exploratory Endpoints

The exploratory endpoints include:

CCI

CCI

6.0 DETERMINATION OF SAMPLE SIZE

Phase 1b

The safety and tolerability of MLN0128 in combination with either exemestane or fulvestrant will be evaluated. Patients will be enrolled as follows:

- In Part 1 of the phase 1b portion of the study, up to 6 patients will be enrolled into the MLN0128 + Exemestane Safety Cohort and up to 6 patients will be enrolled into the MLN0128 + Fulvestrant Safety Cohort. The number of patients is based on clinical considerations.
- In Part 2 of the phase 1b portion of the study, 6 patients will be enrolled into MLN0128 + Exemestane/Fulvestrant Safety Cohort 1, and 6 patients will be enrolled into MLN0128 + Exemestane/Fulvestrant Safety Cohort 2. The number of patients is based on clinical considerations.

Phase 2

The sample size for each cohort in the phase 2 portion of the study is based on a standard Simon two-stage design. A Bayesian predictive probability design was used to allow multiple interim analyses to stop early for futility [1]. See Section 6.0 for sample size assumptions. Up to 56 response-evaluable patients will be enrolled in the Everolimus-Resistant Cohort. In the Everolimus-Sensitive Cohort, up to 48 response-evaluable patients will be enrolled.

7.0 METHODS OF ANALYSIS AND PRESENTATION

7.1 General Principles

All statistical analyses will be conducted using SAS® Version 9.4.

Unless otherwise specified, the baseline value is defined as the value collected at the time closest to, but prior to, the start of study drug administration. Cycle 1 day 1 values are considered pre-dose. Screening values are used for baseline values if a cycle 1 day value is unavailable.

Means and medians will be presented to 1 more decimal place than the recorded data. The standard deviations (SDs) will be presented to 2 more decimal places than the recorded data. Confidence intervals about a parameter estimate will be presented using the same number of decimal places as the parameter estimate.

For the categorical variables, the count and proportions of each possible value will be tabulated. The denominator for the proportion will be based on the number of subjects who provided non-missing responses to the categorical variable. For continuous variables, the number of subjects with non-missing values, mean, median, SD, minimum, and maximum values will be tabulated. Additional statistics will be tabulated for pharmacokinetic data (see Section 7.9.1).

A month is operationally defined to be 30.4375 days.

7.1.1 Data Presentation

Results from the phase 1b and phase 2 portions of the study will be presented separately as follows (unless specified elsewhere):

Phase 1b:

1. Baseline tables (demographics, disease characteristics, prior therapies)

Part 1 MLN0128 Unmilled API			Part 2 MLN0128 Milled API			Phase 1b Total
MLN0128 5 mg QD + Exemestane	MLN0128 5 mg QD+ Fulvestrant	Total	MLN0128 3 mg QD + Exemestane/ Fulvestrant	MLN0128 4 mg QD + Exemestane/ Fulvestrant	Total	
N=6	N=6	N=12	N=6	N=6	N=12	N=24

2. Disposition, Safety

Part 1 MLN0128 Unmilled API			Part 2 MLN0128 Milled API				Phase 1b Total	
MLN0128 5 mg QD + Exemestane	MLN0128 5 mg QD+ Fulvestrant	Total	MLN0128 3 mg QD +Exemestane	MLN0128 3 mg QD + Fulvestrant	Total MLN0128 3 mg QD	MLN0128 4 mg QD+ Exemestane		Total
N=6	N=6	N=12	N=3	N=3	N=6	N=6	N=12	N=24

Phase 2:

1. Disposition, Baseline and Demographic Characteristics, and Efficacy (no total needed)

CONFIDENTIAL

Everolimus Sensitive Cohort			Everolimus Resistant Cohort			Total (except efficacy)
MLN0128 4 mg QD + Exemestane	MLN0128 4 mg QD + Fulvestrant	Sensitive Total	MLN0128 4 mg QD + Exemestane	MLN0128 4 mg QD + Fulvestrant	Resistant Total	

2. Safety

MLN0128 4 mg QD + Exemestane			MLN0128 4 mg QD + Fulvestrant			Total
Everolimus Sensitive Cohort	Everolimus Resistant Cohort	Total	Everolimus Sensitive Cohort	Everolimus Resistant Cohort	Total	

7.1.2 Definition of Study Days

Study Day 1 is defined as the date on which a subject is administered their first dose of the medication. Other study days are defined relative to the Study Day 1 with Day 1 being Study Day 1 and Day -1 being the day prior to Study Day 1.

7.1.3 Conventions for Partial Adverse Event/Concomitant Medication Dates

Missing or incomplete start dates will be imputed based on the algorithm described below:

If the start date has month and year but day is missing, the adverse event will be considered treatment-emergent or the therapy concomitant if both the month and year of the start date are on or after the month and year of the date of the first dose of MLN0128 and on or before the month and year of the date of the last dose of MLN0128 plus 30 days.

- If the start date has year, but day and month are missing, the adverse event will be considered treatment-emergent or the therapy concomitant if the year of the start date is on or after the year of the date of the first dose of MLN0128 and on or before the year of the date of the last dose of MLN0128 plus 30 days.

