### **5.2.1 Phase 1b and Phase 2**

1. Prior anticancer therapy or other investigational therapy within 2 weeks before administration of the first dose of MLN0128 (except for exemestane or fulvestrant, which should be continued). Treatment with everolimus must be discontinued 2 weeks before administration of the first dose of MLN0128.
2. Chronic concomitant therapy with bisphosphonates or denosumab for the prevention of bone metastases. Concomitant treatment with bisphosphonates or denosumab is permitted for treatment of osteoporosis or management of existing bone metastases if initiated at least 4 weeks before administration of the first dose of MLN0128.
3. Exclusion criterion 3 was removed as of Protocol Amendment 6.
4. Initiation of treatment with hematopoietic growth factors, transfusions of blood and blood products, or systemic corticosteroids (either IV or oral steroids, excluding inhalers) within 1 week before administration of the first dose of MLN0128 (patients already receiving erythropoietin on a chronic basis for  $\geq 4$  weeks are eligible).
5. Previous treatment with dual PI3K/mTOR inhibitors or TORC1/2 inhibitors.
6. Manifestations of malabsorption due to prior gastrointestinal (GI) surgery, GI disease, or for an unknown reason that may alter the absorption of MLN0128.
7. Poorly controlled diabetes mellitus defined as glycosylated hemoglobin (HbA1c)  $> 7\%$ ; patients with a history of transient glucose intolerance due to corticosteroid administration may be enrolled in this study if all other inclusion/exclusion criteria are met.
8. Other clinically significant co-morbidities, such as uncontrolled pulmonary disease, active central nervous system disease, active infection, or any other condition that could compromise participation of the patient in the study.
9. Known human immunodeficiency virus infection.

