#### **6.4 Excluded Concomitant Medications and Procedures**

All prescription and over-the-counter medications, including influenza vaccines, taken by a patient as of the first MLN0128 administration through 30 days following the last dose will be recorded on the designated case report form.

The following medications/therapies are prohibited during the study:

- Other investigational agents, including mTOR, PI3K, and AKT inhibitors.
- Other anticancer therapies, including chemotherapy, immunotherapy, radioimmunotherapy, targeted agents, radiation, or surgery (patients can have palliative radiation or surgery during the study for pre-existing lesions).
- Systemic corticosteroids (either IV or oral steroids, excluding inhalers), unless necessary for treatment of an MLN0128-related AE (eg, rash).
- Strong CYP1A2 inhibitors and CYP inducers should be administered with caution and at the discretion of the investigator (see Section 14.4 for a list of these agents).
- Antiepileptic drugs for patients with a history of treated brain metastasis.
- Concomitant administration of any proton pump inhibitor (PPI) is not permitted during the study. Patients receiving PPI therapy before enrollment must stop using the PPI for 7 days before their first dose of study drugs. Examples of PPIs include omeprazole, esomeprazole, pantoprazole, lansoprazole, and rabeprazole.
- Histamine H2 receptor antagonists may be allowed, if needed provided that the histamine H2 receptor antagonist is not taken within 12 hours before and within 6 hours after study drug administration. Patients receiving histamine H2 receptor antagonists before enrollment must stop using these medications for at least 24 hours before their first dose of study drug. Examples of histamine H2 receptor antagonists include ranitidine, famotidine, and nizatidine. Cimetidine, a moderate CYP1A2 inhibitor, is not recommended as a first choice H2 receptor antagonist (see Section 14.4).

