7.6 Medication History and Concomitant Medications

No summary for medication history.

Concomitant medications will be coded using the World Health Organization (WHO) Drug Dictionary. The number and percentage of patients taking concomitant medications will be tabulated by WHO standardized medication name (generic name).

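### SAP 7.1.3 decides whether a therapy with a partial start date is concomitant by when it began, so long-term drugs still in use on study can drop out of the concomitant-medication table

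*SAP*

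**What the plan says.** SAP 7.1.3 covers partial dates for adverse events and medications together. It opens with "Missing or incomplete start dates will be imputed based on the algorithm described below" and then gives two cases.

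- **Day missing.** The event is treatment-emergent "or the therapy concomitant if both the month and year of the start date are on or after the month and year" of first MLN0128 dose, and also "on or before the month and year of the date of the last dose of MLN0128 plus 30 days".
- **Day and month missing.** The same approach is taken by year. For drugs the test reads: "the therapy concomitant if the year of the start date is on or after the year of the date of the first dose of MLN0128", with an upper limit by year in the same way.

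Neither case refers to a stop date or to whether the therapy is ongoing. Neither covers a start date that is wholly missing, although the opening sentence mentions one.

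SAP 7.6 tabulates patients taking concomitant medications by generic name. It does not define concomitant any further, and it plans no summary of medication history.

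Protocol 6.4 describes what reaches the database: all medications "taken by a patient as of the first MLN0128 administration through 30 days following the last dose will be recorded". Protocol 7.4.10 uses the same window. Both turn on use in the window, not on starting in it.

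Protocol 5.2.1, exclusion criterion 2, allows bisphosphonates or denosumab for osteoporosis or existing bone metastases "if initiated at least 4 weeks before administration of the first dose of MLN0128".

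**The concern.** One date window serves two different concepts. Whether an adverse event is treatment-emergent depends on when it began. Whether a drug is concomitant depends on whether it was taken during treatment, and a drug begun years earlier and never stopped qualifies as fully as one begun on Day 10. A start-date test therefore works against long-term medication, and long-standing drugs are the ones whose start date a patient is least likely to recall exactly.

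The drugs exposed matter for reading the safety data. Hyperglycemia and hyperlipidemia have their own management tables in the protocol, so a reader will want to see glucose- and lipid-lowering drugs. Strong CYP1A2 inhibitors and CYP inducers are left to investigator caution under Protocol 6.4, and this table is the only planned summary of their use. Bone agents are exposed as well. Any error goes in one direction, towards undercounting.

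**Working it through.** The documents give no figure to reproduce, so the check applies the rule as written and then sets it beside the other sections.

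**1. The rule on example dates.** Assumed for illustration: first dose 15 Jun 2016 and last dose 10 Dec 2016, so last dose plus 30 days is 9 Jan 2017. The SAP window is then Jun 2016 to Jan 2017 when the day is missing, and 2016 to 2017 when only the year is known. Each drug below is taken on study. The overlap rule asks whether use overlaps the period from first dose to last dose plus 30 days.

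| Recorded start | Meets SAP 7.1.3 | Meets overlap rule |
|---|---|---|
| 2012 | No | Yes |
| 2015 | No | Yes |
| Mar 2016 | No | Yes |
| May 2016 | No | Yes |
| Jun 2016 | Yes | Yes |
| 2016 (year only) | Yes | Yes |
| Aug 2016 | Yes | Yes |

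The rule fails a partial date in an earlier month (day missing) or an earlier year (day and month missing). It keeps a year-only date in the first-dose year. The split in this table reflects the dates chosen and does not estimate how often the problem occurs.

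**2. Bone agents.** Let first dose fall on day d of a month. A start at least 28 days earlier falls on day d − 28 at the latest. It shares the calendar month with first dose only if d − 28 ≥ 1, that is d ≥ 29. So unless first dose falls on day 29, 30 or 31, every protocol-compliant start lies in an earlier month, and with the day missing it fails the rule. With first dose on 15 Jun 2016, the latest compliant start is 18 May 2016, recorded at best as May 2016.

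**3. Is the drug recovered elsewhere?**

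- SAP 7.6 summarizes no medication history, and SAP 7.5 no medical history.
- SAP 7.6.1 covers prior surgery, radiation and antineoplastic therapy only.
- The subject-level listings in SAP 9.0 include none for concomitant medications.

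A drug that fails 7.1.3 therefore appears in no specified output. Protocol 8.1.4, in contrast, promises that all available safety data will be listed and tabulated.

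**The case against.** The strongest reply is that SAP 7.1.3 says *if*, not *only if*. It names cases that count and never states that earlier-started therapies are excluded. Collection is already limited to on-study use, and neither SAP 7.6 nor Protocol 8.1.8 puts a start-date condition on the table. A programmer who tabulated every recorded medication would lose nothing. This stands in part: exclusion is the natural reading, not an express instruction. It does not dispose of the point. If every collected record counts regardless, the therapy clause does almost nothing, and a clause in a date-classification rule will be read as classifying.

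Several stronger readings are tempting but unsupported.

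- **The same drug with a complete date is counted.** This is a fair inference from Protocol 6.4 and 7.4.10, but the SAP gives no concomitance rule for complete dates.
- **Acid reducers are lost.** Protocol 6.4 prohibits proton pump inhibitors on study, with a 7-day stop before first dose, and has H2 antagonists stopped at least 24 hours before it. Continuous use of either across first dose is outside the protocol, so they are poor examples.
- **Every such bone-agent patient is lost.** Protocol 6.5 says bisphosphonates should be given after Cycle 1, so a resumed course may carry a new on-study record. A patient with a second record of the same generic drug that meets the rule is still counted.
- **The safety analyses are biased.** The table is descriptive and not split by baseline versus on-study start. No planned analysis of glucose, lipids or pharmacokinetics is described as using it. Drugs started on study to treat a toxicity meet the rule, and eligibility limits baseline glycemia (fasting glucose at most 130 mg/dL; HbA1c above 7% excluded).

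**Conclusion.** The point holds as a defect in a stated rule. SAP 7.1.3 applies an adverse-event onset window to therapies and, on its natural reading, leaves out drugs that the protocol records because they were used on study. It affects partial start dates in a month or year before that of first dose, and one descriptive safety table. The primary endpoint, the futility boundaries and dose decisions are untouched.

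The size of the undercount cannot be derived. For one drug, the tabulated share is the true share × (1 − the fraction of users lost to the rule), and the documents give neither term. A reader might put in, say, 40% users with 25% to 60% lost, giving 40% × 0.75 = 30% down to 40% × 0.40 = 16%. Those inputs are pure assumption, and the sum further supposes one record per patient, so it is not an estimate for this trial.

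The conclusion assumes that the therapy clause is meant to classify and that no programming specification overrides it. It is worth correcting because the fix is cheap and the error runs one way.

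**What to change.** Split SAP 7.1.3. Keep the start-date window for adverse events only. For therapies, state that a therapy is concomitant unless either:

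- its stop date, taken as the latest possible date if partial, is before first MLN0128 dose; or
- its start date, taken as the earliest possible date if partial, is more than 30 days after last MLN0128 dose.

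Add that a therapy flagged as ongoing, or one whose start date is wholly missing, is concomitant unless it is known to have stopped before first dose. This also closes the gap for missing start dates.

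The cost is about one SAP sentence and a change to one derived flag. No new data should be needed: Protocol 6.5 already has medications added or discontinued on study entered in the eCRF, assuming the form holds a stop date or ongoing status. No efficacy result changes.

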7.1.4 Conventions for Other Partial Dates

Missing or incomplete dates recorded during the screening visits (e.g date of initial diagnosis) will be imputed based on the algorithm described below:

- If only the day-component is missing, the first day of the month will be used if the year and the month are the same as those for the first dose of study drug. Otherwise, the fifteenth will be used.
- If only the year is present, and it is the same as the year of the first dose of study drug, the fifteenth of January will be used unless it is later than the first dose, in which case the date of the 15th of January will be used.

- If only the year is present, and it is not the same as the year of the first dose of study drug, the fifteenth of June will be used, unless other data indicates that the date is earlier.

7.2 Analysis Sets

7.2.1 Safety Population

Safety population: patients who receive at least 1 dose of study drug. All safety analyses will be performed using the safety population.

7.2.2 Response-Evaluable Population

Response-evaluable population (phase 2 only): patients who receive at least 1 dose of study drug and have measurable disease at baseline.

7.2.3 Pharmacokinetics Population

Pharmacokinetic population: patients with sufficient dosing and PK data to reliably estimate PK parameters. PK analyses will be performed using the PK population.

7.3 Disposition of Subjects

The date first subject signed ICF, date of last subject's last visit/contact, date of last subject's last procedure for collection of data for primary endpoint, MedDRA Version, WHODrug Version, and SAS Version will be generated in a summary table.

For the phase 1 portion the number of patients in the safety population, in the pharmacokinetics population, and the reason study drug was discontinued will be summarized.

For the phase 2 portion the number of patients in the safety population, in the response-evaluable population, the dose level of exemestane or fulvestrant at study entry, the reason study drug was discontinued, and the end of study reasons will be summarized.

All percentages will be based on the number of patients in the safety population.

The number of subjects enrolled by region, country and site will be summarized:

North America
- United States

Europe
- Belgium
- France

7.4 Demographic and Other Baseline Characteristics

Summaries of demographic and baseline characteristics will be presented for subjects in the safety population.

The demographic characteristics consist of:

- Age at date of informed consent (continuous)
- Age category 1.
 - <65 years.
 - ≥65 years.
- Age category 2.
 - Adults (18-64 years).
 - From 65 to 84 years.
 - 85 years and over.
- Height (cm).
- Weight (kg) [at screening if available, otherwise use C1D1].
- Ethnicity.
- Race.

Baseline characteristics consist of:

- Baseline ECOG performance status.
- Histological subtype (Basal, Luminal A, Luminal B, Normal Breast-like).
- Time since initial diagnosis (months) [(date of first dose – date of initial diagnosis)/30.4375].
- Stage of disease at initial diagnosis.
- Number and percent positive for each marker: PR, C-myc amplification, BRCA1, BRCA2, and EGFR.
- Number and percent positive for PTEN (from tumor samples).

7.5 Medical History and Concurrent Medical Conditions

No summary for medical history and concurrent medical conditions.

7.6 Medication History and Concomitant Medications

No summary for medication history.

Concomitant medications will be coded using the World Health Organization (WHO) Drug Dictionary. The number and percentage of patients taking concomitant medications will be tabulated by WHO standardized medication name (generic name).

7.6.1 Prior Therapies

The number and percentage of patients with prior surgery, prior radiation, and prior antineoplastic therapies will be summarized. The following will be summarized for those patients with prior antineoplastic therapies:

- Prior therapy received (PTDECOD in PT dataset).
- Number of prior therapy regimens (PTGRPID in PT dataset).
- Best response to most recent prior therapy.

7.7 Study Drug Exposure and Compliance

7.7.2 Extent of Exposure

The overall treatment duration in weeks (date of last dose – date of first dose + 1/ 7), number of treated cycles (distribution and summary statistics), cumulative dose for each study drug, average daily dose in mg/day [cumulative dose in mg / duration of treatment in days] for MLN0128 and exemestane, planned cumulative dose for each study drug, and the relative dose intensity for each study drug will be summarized for patients in the safety population.

A treated cycle is defined as a cycle in which the patient receives any amount of MLN0128 (actual dose greater than zero for at least one of the dosing days in the cycle).

The cumulative dose for MLN0128 and exemestane (mg) is the sum of all doses (mg) administered to a subject during the treatment period.

Relative dose intensity = [cumulative dose / planned cumulative dose] * 100.

For MLN0128 and exemestane the relative dose intensity is calculated as:

[cumulative dose in mg / assigned dose level (mg) at the start of the study * duration of treatment in days] * 100.

For fulvestrant the relative dose intensity is calculated as:

[cumulative dose in mg / assigned dose level (mg) at the start of the study * number of treatment cycles] * 100.

